5.2. Exclusion Criteria

Participants are excluded from the study if any of the following criteria apply

Prior or Concomitant Diseases:

1. History of malignancy other than the disease under study.

EXCEPTION NOTE: Participants who have been disease-free for 5 years, or participants with a history of completely resected non-melanoma skin cancer or successfully treated in situ carcinoma are eligible. Participants with second malignancies that are indolent or definitively treated may be enrolled even if less than 5 years have elapsed since treatment. Consult GSK Medical Monitor if unsure whether second malignancies meet requirements specified above

2. Primary central nervous system (CNS) tumors, Glioblastoma multiforme (GBM), symptomatic or untreated leptomeningeal or brain metastases or spinal cord compression.

EXCEPTION NOTE: Participants previously treated for these conditions that have had stable CNS disease (verified with consecutive imaging studies) for >1months, are asymptomatic and off corticosteroids, or are on stable dose of corticosteroids for at least 1 month prior to study Day 1 are permitted. Stability of brain metastases must be confirmed with imaging. Participant treated with gamma knife therapy can be enrolled 2 weeks post-procedure as long as there are no post-procedure complications/they are stable.

3. Any severe or uncontrolled systemic diseases (e.g., unstable or uncompensated respiratory, hepatic, renal, cardiac disease, or clinically significant bleeding episodes, or active infection).
4. Any serious and/or unstable pre-existing medical, psychiatric disorder, or other conditions that could interfere with participant's safety, obtaining informed consent or compliance to the study procedures, in the opinion of the Investigator.

5. Any clinically significant gastrointestinal (GI) abnormalities that may alter absorption such as malabsorption syndrome or major resection of the stomach and/or bowels.
6. History of known human immunodeficiency virus (HIV) infection or positive HIV test result at screening.
7. Presence of hepatitis B surface antigen (HBsAg) or positive hepatitis C antibody test result at screening to first dose of study intervention.

NOTE: Participants with positive Hepatitis C antibody due to prior resolved disease can be enrolled only if a confirmatory negative Hepatitis C RNA polymerase chain reaction (PCR) is obtained.

8. Any of the following cardiac abnormalities:
 - a) Uncontrolled high blood pressure.
 - b) Any history of coronary artery disease, including acute coronary syndromes, myocardial infarction, unstable angina, and history of coronary angioplasty, or stenting
 - c) Presence of a cardiac pacemaker or implanted defibrillator.
 - d) AV-block (asymptomatic 2nd degree Type II or 3rd degree and any degree AV block if related to heart disease or if symptomatic), RBBB (right bundle branch block), LBBB (left bundle branch block), and any fascicular hemiblocks.
 - e) A QRS interval at Screening or Baseline ≥ 110 msec.
 - f) Patients with any symptomatic or sustained arrhythmias (past or present), including but not limited to:
 - Atrial fibrillation.
 - Atrial flutter
 - Ventricular tachycardia
 - Ventricular fibrillation
 - Supraventricular tachycardia
 - g) Current or past congestive heart failure.
 - h) Evidence of a left ventricular ejection fraction below the institutional lower limit of normal on Screening echocardiogram.
 - i) Evidence of significant structural heart disease on echocardiography at Screening (including any valvular disease greater than “mild” in severity)
 - j) Cardiac troponin > upper limit of the reference range at Screening.

Prior or Concomitant Anti-cancer Therapies

9. Treatment with any local or systemic anti-neoplastic therapy or investigational anti-cancer agent within 14 days or 4 half-lives, whichever is longer, up to a maximum wash-out period of 28 days prior to initiation of study drug administration

EXCEPTION NOTE: Anti-androgen therapies for prostate cancer, such as bicalutamide, must be stopped 28 days prior to first dose of GSK3368715. Second-line hormone therapies such as enzalutamide or abiraterone should be stopped 14 days prior to enrolment. Participants with prostate cancer may remain on (i) luteinizing hormone-releasing hormone (LHRH) agonists or antagonists and/or (ii) low-dose prednisone or prednisolone (up to 10 mg/day).

Nitrosureas and mitomycin C must be stopped within 42 days prior to first dose of GSK3368715.

10. Allogeneic hematopoietic stem-cell transplantation
11. Toxicities from previous anti-cancer therapies have not resolved to baseline or NCI-Common terminology criteria for adverse events (CTCAE) v5 \leq Grade 1 (except fatigue and alopecia [permissible at any grade] and peripheral neuropathy [which must be \leq Grade 2]) at the time of starting study intervention.

Prior or Concomitant Therapies:

12. Major surgery (i.e. requiring general anesthesia) within 3 weeks before screening, or not fully recovered from major surgery, or major surgery planned during study participation

EXCEPTION NOTE: Planned surgical procedures to be conducted under local anesthesia are allowed.

13. Prior organ transplantation
14. Current use of a prohibited medication or planned use of any forbidden medications during intervention with GSK3368715
15. History of sensitivity to any of the study medications, or components thereof or a history of drug or other allergy that, in the opinion of the investigator or Medical Monitor, contraindicates their participation.
16. Participant is considered high-risk for VTE as defined by either Khorana Score of ≥ 3 (see [Appendix 13](#)), or prior medical history of VTE. Note: Participants with Khorana score of 2 should be considered for prophylactic anticoagulation per current ASCO guidelines ([Key, 2019](#)) if deemed appropriate by the investigator.

5.3. Lifestyle Restrictions**5.3.1. Meals and Dietary Restrictions**

On serial PK days (Day 1, Day 8 and Day 15), participants should fast from 8 hours prior to dose until 2 hours after dose. On all other days, GSK3368715 should be administered on an empty stomach at approximately the same time of day (± 4 h), with no food for 1 hour before and 2 hours after each dose. Requirements for fasting before and after dosing may be modified based on available PK, PD and safety data. The exact timing of the meals administered will be recorded on serial PK days.

On serial PK days, 8 and 15 and for two days prior to each serial PK day other than Day 1 (Days 6 and 7 and 13 and 14), participants should attempt to take GSK3368715 within a 1 hour window (i.e., 23-25 hours) after the last dose.

Participants will abstain from alcohol, tobacco, caffeine- or xanthine-containing products (eg, coffee, tea, cola drinks, and chocolate) for 24 hours before the start of dosing until after collection of the final PK and/or PD sample on Day 16. In addition, participants should also abstain from ingesting these products prior to clinic visits on days scheduled for periodic PK and PD sample collection throughout the study.

Refrain from consumption of red wine, seville oranges, grapefruit or grapefruit juice for at least 24 hours before the start of study intervention until after the final dose.

For participants in the food effect sub-study, the administration of GSK3368715 on the 'fed'/'fasted' days will be performed as described in Section [4.1.1.1](#). For all other days, it will be administered as described above.

5.4. Screen Failures

Screen failures are defined as participants who consent to participate in the clinical study but are not subsequently entered in the study. A minimal set of screen failure information is required to ensure transparent reporting of screen failure participants to meet the Consolidated Standards of Reporting Trials (CONSORT) publishing requirements and to respond to queries from regulatory authorities. Minimal information includes demography, screen failure details, eligibility criteria, and any serious adverse events (SAEs).

Individuals who do not meet the criteria for participation in this study (screen failure) may be rescreened once. Rescreened participants should be assigned the same participant number as for the initial screening if rescreening for same arm of study. Please refer to the Study Reference Manual for more details.

6. STUDY INTERVENTION

Study intervention is defined as any investigational intervention(s), marketed product(s), placebo, or medical device(s) intended to be administered to a study participant according to the study protocol. The term ‘study intervention’ is used throughout the protocol to describe any combination of products received by the participant as per the protocol design.

6.1. Study Intervention(s) Administered

The participants in each cohort will receive GSK3368715 orally, administered as either a capsule or tablet formulation (please refer to Section 1.2 and Section 1.3 for more detail).

During the DLT observation period, participants will only receive capsules, and may receive the tablet formulation if the participant continues on treatment at the end of Part 1.

Table 7 Study intervention

ARM Name	GSK3368715
Intervention Name	N/A
Type	Drug
Dose Formulation	
 1. API in Hydroxypropyl Methylcellulose (HPMC) Capsule 2. Immediate release (IR) white film-coated tablet containing API and excipients
Unit Dose Strength(s)	
 1. Capsule: 25 mg, 100 mg, 250 mg as free-base drug substance 2. Tablet: 50 mg, 100 mg and 250 mg as the free-base drug substance
Dosage Level(s)	As required by protocol
Route of Administration	Oral
IMP and NIMP	IMP (GSK3368715)
Sourcing	Provided centrally by the Sponsor
Packaging and Labelling	Study intervention will be labelled as required as per country requirement
Current/Former Name(s) or Alias(es)	N/A

6.2. Dose Modification

Safety management guidelines, including dose modification algorithms, are provided. Please note, in cases where the investigator is directed to permanently discontinue study intervention, these instructions are mandatory as described in Section 7.

An overview of the available dose modification guidelines is presented in [Appendix 12](#).

All AEs are to be graded according to NCI-CTCAE, version 5. All dose modifications and the reason(s) for the dose modification must be documented in the eCRF.

Investigators should refer to the IB for GSK3368715 [GlaxoSmithKline Document Number [2017N334333_02](#)] and for additional information regarding the background of the drug and the management of other AEs or potential safety-related issues.

In case a dose modification is necessary, the dose level of one or both study interventions may be changed as determined by the investigator and sponsor/medical monitor.

6.3. Method of Intervention Assignment

All screened participants will be identified by a unique participant number that will remain consistent for the duration of the study. Upon completion of all of the required screening assessments, eligible participants will be registered into the study by the investigator or authorized site staff. See SRM for additional information on screening and enrollment procedures.

6.4. Blinding

This is an open-label study.

6.5. Preparation/Handling/Storage/Accountability

1. The investigator or designee must confirm appropriate temperature conditions have been maintained during transit for all study intervention received and any discrepancies are reported and resolved before use of the study intervention.
2. Only participants enrolled in the study may receive study intervention and only authorized site staff may supply or administer study intervention. All study interventions must be stored in a secure, environmentally controlled, and monitored (manual or automated) area in accordance with the labeled storage conditions with access limited to the investigator and authorized site staff.
3. The investigator, institution, or the head of the medical institution (where applicable) is responsible for study intervention accountability, reconciliation, and record maintenance (i.e., receipt, reconciliation, and final disposition records).
4. Further guidance and information for the final disposition of unused study intervention are provided in the SRM.

5. Under normal conditions of handling and administration, study intervention is not expected to pose significant safety risks to site staff. Precaution will be taken to avoid direct contact with the study intervention.
6. A Material Safety Data Sheet (MSDS) describing occupational hazards and recommended handling precautions will be provided to the investigator. In the case of unintentional occupational exposure notify the monitor, Medical Monitor and/or GSK study contact.

6.6. Intervention Compliance

At each visit, an evaluation of participant compliance with taken medication will be performed. The investigator will make every effort to bring non-compliant participants into compliance.

Compliance with GSK3368715 and other study interventions provided will be assessed through querying the participant during the site visits and documented in the source documents and eCRF.

A record of the number of GSK3368715 capsules and other study interventions dispensed to and taken by each participant must be maintained and reconciled with study intervention and compliance records. Intervention start and stop dates, including dates for intervention interruptions and/or dose reductions will also be recorded in the eCRF.

6.7. Concomitant Therapy

Any medication or vaccine (including over-the-counter or prescription medicines, vitamins, and/or herbal supplements) that the participant is receiving at the time of enrolment or receives while on study intervention and for 30 days after last dose must be recorded in the eCRF along with:

- reason for use
- dates of administration including start and end dates
- dosage information including dose and frequency

The Medical Monitor should be contacted if there are any questions regarding concomitant or prior therapy.

Participants should receive full supportive care during the study, including transfusion of blood and blood products, and intervention with antibiotics, antiemetics, antidiarrheals, and analgesics, as appropriate.

Participants will be instructed to inform the investigator prior to starting any new medications from the time of first dose of study intervention until the end of the study (Final Study Visit).

A complete list of all prior anti-cancer therapies will be recorded in the eCRF.

If future changes are made to the list of permitted/prohibited medications, formal documentation will be provided by GSK and stored in the study file. The SRM will be

updated to include this information. Any such changes will be communicated to the investigative sites in the form of a letter.

The prophylactic use of low molecular weight heparin and oral anticoagulation using Factor Xa inhibitors such as Apixaban and Rivaroxaban is allowed on trial. Current ASCO 2019 Guidelines (Key, 2019) and the bleeding risk associated with above agents should be considered.

If a participant experiences a VTE and requires therapeutic anticoagulation, treatment should be initiated without delay following best medical practice, GSK3368715 should be held and the situation should be discussed with the GSK medical monitor (see Appendix 12, Table 14).

6.7.1. Prohibited Medications/Therapy

- Immunotherapy not specified in this protocol
- Chemotherapy not specified in this protocol
- Radiotherapy (strictly palliative radiotherapy while on study treatment may be acceptable if discussed with and approved by the sponsor).
- Investigational interventions other than with GSK3368715.
- Anticoagulation with oral Vitamin K antagonists such as Warfarin.

6.7.2. Cautionary Medications

Co-administration of GSK3368715 and substrates of CYP2D6 should be avoided in order to prevent inadvertent over-exposure to these agents. GSK3368715 inhibits CYP2D6 *in vitro* (IC₅₀ = 22.6 μM), indicating a potential for interaction between GSK3368715 and CYP2D6 substrates.

No *in vitro* CYP phenotyping data are available for GSK3368715. In the absence of these data, potent inhibitors or inducers of CYP3A4 isoenzymes should not be co-administered with GSK3368715.

6.8. Intervention After the End of the Study

The investigator is responsible for ensuring that consideration has been given for the post-study care of the participant's medical condition.

Refer to SOA (Section 1.3) for follow-up assessments of participants who are to be followed for disease progression and/or survival after they permanently discontinue from study intervention.

6.9. Dose Delay

If there is a dose delay between 1 and 3 days, the procedures at the original scheduled visit (including dosing) should be performed as soon as possible. If the delay is >3 days, the visit and dose(s) will be considered missed. The procedures at the next scheduled visit

should be performed. Participants with dosing delays equivalent to 14 consecutive missed doses should discontinue study intervention(s) unless the treating investigator and Sponsor agree there is strong evidence supporting continued intervention.

7. DISCONTINUATION OF STUDY INTERVENTION AND PARTICIPANT DISCONTINUATION/WITHDRAWAL

Participants will receive study intervention until one of the following events occur earlier: disease progression (as determined by [Appendix 10](#)), death or unacceptable toxicity, including meeting stopping criteria for liver chemistry or cardiac parameters defined in [Section 7.1.1](#) and [Section 7.1.2](#).

7.1. Discontinuation of Study intervention

In addition to the above, study intervention may be permanently discontinued for any of the following reasons:

- Deviation(s) from the protocol
- Request of the participant or proxy (withdrawal of consent by participant or proxy)
- Investigator's discretion
- Participant is lost to follow-up
- Study is closed or terminated.
- Criteria described in [Section 6.9](#) (Dose Delay)
- Female participant who becomes pregnant while on study intervention
- Criteria for discontinuation of study intervention(s) as described in [Section 6.2](#) (Dose Modification Guidelines) have been met
- Criteria described in [Section 7.1.2](#) and [Section 7.1.3](#) (QTc or QRS Stopping Criteria and LVEF Stopping Criteria) have been met
- Criteria described in [Section 7.1.4](#) (Stopping Rules for Clinical Deterioration) have been met

If study intervention is permanently discontinued, the participant will remain in the study to be evaluated for safety and efficacy. See the SOA for data to be collected at the time of discontinuation of study intervention. The assessments required at the TDV should be completed within 30 days of the last dose of study intervention(s). The primary reason study intervention was permanently discontinued must be documented in the participant's medical records and electronic case report form (eCRF).

All participants who permanently discontinue study intervention(s) without disease progression will be followed for progression according to the protocol schedule until

- New anti-cancer therapy is initiated
- Disease progression
- Death, or
- Participant has been followed for 2 years after stopping intervention.

All participants who have disease progression will be followed for survival and new anti-cancer therapy (including radiotherapy). Survival follow-up will continue from the time of study drug discontinuation until the earliest of the following: 1.) death or 2.) a maximum time period of 2 years has passed after discontinuing study intervention or 3.) study is closed for further follow-up (expected when 70% of participants in the last part of the study have progressed or died). If participants are unable or unwilling to attend clinic visits during follow-up, contact to assess survival may be made via another form of communication (e.g., phone, email, etc.).

If the participant voluntarily discontinues from intervention due to toxicity, ‘adverse event (AE)’ will be recorded as the primary reason for permanent discontinuation on the eCRF.

[figure not shown]
Once a participant has permanently discontinued from study intervention, the participant will not be allowed to be retreated.

All participants who discontinue from study intervention will have safety assessments at the time of discontinuation and during post-study intervention follow-up as specified in Schedule of Activities Table (see Section 1.3).

7.1.1. Liver Chemistry Stopping Criteria

Liver chemistry stopping and increased monitoring criteria have been designed to assure participant safety and evaluate liver event etiology.

Discontinuation of study intervention for abnormal liver tests is required when a participant meets the conditions outlined in [Figure 3](#).

Figure 3 Liver Chemistry Stopping Criteria

Liver Safety Required Actions and Follow-up Assessments Section can be found in [Appendix 6](#).

7.1.1.1. Study Intervention Restart or Rechallenge after liver stopping criteria met

If participant meets liver chemistry stopping criteria do not restart/rechallenge participant with study intervention unless:

- GSK Medical Governance approval **is granted**
- Ethics and/or IRB approval is obtained, if required, and
- Separate consent for intervention restart/rechallenge is signed by the participant

Refer to [Appendix 6](#) for full guidance.

7.1.2. QTc Stopping Criteria

For trial eligibility and discontinuation, ideally the same QT correction formula will be used for *all* participants within a single trial. However, GSK does recognize that because multiple sites from different countries may participate in a single trial, this may not always be possible since QT correction formulae pre-programmed by different manufacturers within ECG machines tend to vary. In these situations, the same QT correction formula must be used throughout the trial for an individual participant.

- QTcF > 500 msec

OR

- Change from baseline of QTc > 60 msec

The QTcF correction formula *must* be used for *each individual participant* to determine eligibility for and discontinuation from the study. This formula may not be changed or substituted once the participant has been enrolled.

The QTc should be based on single or averaged QTcF values of triplicate electrocardiograms obtained over a brief (e.g., 5-10 minute) recording period.

See the SoA for data to be collected at the time of intervention discontinuation and follow-up and for any further evaluations that need to be completed.

7.1.3. QRS Interval Stopping Criterion

An increase in the QRS interval of > 20 ms from baseline.

7.1.4. PR Interval Stopping Criteria

An increase in the PR interval to >250 msec in participants without pre-existing AV-block.

Stopping Rules for Clinical Deterioration

In order to adequately assess the antitumor effect of epigenetic agents, participants experiencing apparent progression as defined by RECIST version 1.1 guidelines may continue to receive intervention until progression is confirmed at the next imaging assessment at least 4 weeks later as indicated by RECIST guidelines. These considerations should be balanced by clinical judgment as to whether the participant is clinically deteriorating and unlikely to receive benefit from continued study intervention. Participants who had documented reduction in tumor size or a prolonged period of stable disease may be eligible for additional intervention with GSK3368715 at the time of relapse/progression if determined to be deriving clinical benefit in the opinion of the investigator and with sponsor approval.

In cases where deterioration was assessed in the investigator's opinion to have occurred after a clinical event and is attributable to disease progression, is unlikely to reverse with continued study intervention or managed by supportive care (e.g., bisphosphonates and/or bone directed radiotherapy, thoracentesis, or paracentesis for accumulating effusions), study intervention should be discontinued. The decision to stop intervention should be discussed with the Sponsor's Medical Monitor. Examples of events that may, in the investigator's opinion, indicate a lack of clinical benefit include, but are not limited to the following:

- ECOG PS decrease of at least 2 points from baseline
- Skeletal related events defined by the following:
 - pathologic bone fracture in the region of cancer involvement
 - cancer related surgery to bone, and/or
 - spinal cord or nerve root compression
- Development of new CNS metastases

Any setting where the initiation of new antineoplastic therapy has been deemed beneficial to the participant even in the absence of any such documented clinical event.

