8.2.3. Electrocardiograms

Triplicate 12-lead ECG will be obtained as outlined in the SoA (Section 1.3) using an ECG machine that automatically calculates the heart rate and measures PR, QRS, QT, and QTc intervals. Refer to Section 7.1.2 for QTc withdrawal criteria and additional QTc readings that may be necessary. In cases with equivocal findings a site cardiologist may aid in determining eligibility.

- At each time point at which triplicate ECG are required, three individual ECG tracings should be obtained as closely as possible in succession, but no more than 2 minutes apart. The full set of triplicates should be completed in less than 4 minutes.

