10.12.1. Management of Selected Toxicities

Table 14 Dose Adjustment/Stopping Safety Criteria

Toxicity	Dose Adjustment/ Stopping Criteria	Management Guidelines
Thrombocytopenia	Grade 1 & 2	Continue dosing at same dose level with weekly or more frequent monitoring as necessary
	Grade 3	
 Hold GSK3368715 until resolved to Grade ≤ 1 within ≤ 14 days Monitor complete blood count (CBC) at least twice a week Discuss with GSK Medical Monitor Re-start GSK3368715 at a reduced dose Discontinue GSK3368715 if not resolved to Grade ≤ 1 within ≤ 14 days
	Grade 4	
 Discontinue GSK3368715 Monitor CBC every 2-3 days.
Anemia	Grades 1 & 2	Continue dosing at same dose level with weekly or more frequent monitoring as necessary
	Grade 3	
 Hold GSK3368715 until resolved to Grade ≤ 1 within ≤ 14 days. Transfuse and treat as necessary. Monitor CBC at least twice a week. Discuss with GSK Medical Monitor. Re-start GSK3368715 at a reduced dose. Discontinue GSK3368715 if not resolved to Grade ≤ 1 within ≤ 14 days.
	Grade 4	
 Discontinue GSK3368715. Transfuse and treat as necessary. Monitor CBC every 2-3 days.
PR Interval	An increase in the PR Interval to >250 msec	
 This interval should be based on the average of the triplicate ECGs Discontinue GSK3368715 Contact the medical monitor Maintain proper electrolytes similar to recommendations for QTcF

Toxicity	Dose Adjustment/ Stopping Criteria	Management Guidelines
QRS Interval	An increase of >20% from baseline	
 This interval should be based on the average of the triplicate ECGs Discontinue GSK3368715 Contact the medical monitor Maintain proper electrolytes similar to recommendations for QTcF
QTcF	If >30msec and < 60 msec change from baseline AND manual QTcF <500 msec (average of three ECGs over at least 15 minutes)	
 Continue current dose of GSK3368715 
 Supplement electrolytes, particularly potassium and magnesium, to recommended levels: 
 Maintain serum potassium > 4 mol/L Maintain serum magnesium levels >0.85 mmol/L Discontinue any concomitant medications with potential for QTcF prolongation. Consider 24 hour or longer telemetry monitoring if clinically indicated.

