	If ≥ 60 msec change from baseline occurs OR QTcF ≥ 500 msec (average of three ECGs over at least 15 minutes)	Discontinue GSK3368715 and notify the GSK Medical Monitor.
Liver		Refer to procedures outlined in Section 7.1.1 Liver Safety Required Actions and Follow up Assessments
Diarrhea	Grade 1	Initiate supportive care including loperamide.
	Grade 2	
 Initiate supportive care including loperamide. Consider hold of GSK3368715 Discuss with GSK Medical Monitor.
	Grade 3	
 Treat as above plus consider intravenous (IV) hydration, hospital admission and prophylactic antibiotics as appropriate. Hold GSK3368715 Discuss with GSK Medical Monitor. Re-start GSK3368715 at a reduced dose Discontinue GSK3368715 if not resolved to Grade ≤ 1 within ≤ 14 days
	Grade 4	
 Above plus consider intravenous (IV) hydration, hospital admission and prophylactic antibiotics as appropriate. Discontinue GSK3368715

Toxicity	Dose Adjustment/ Stopping Criteria	Management Guidelines
Nausea/Vomiting	Grade 1	
 Initiate supportive care with antiemetics as necessary.
	Grade 2	
 Initiate supportive care with antiemetics as necessary Consider hold of GSK3368715 until resolved to Grade \leq 1 within \leq 14 days Discuss with GSK medical monitor
	Grade 3	
 Supportive care as above, plus consider intravenous (IV) hydration, hospital admission and IV nutrition as appropriate. Hold GSK3368715 until resolved to Grade \leq 1 within \leq 14 days Discuss with GSK Medical Monitor. Re-start GSK3368715 at same dose if resolved within \leq 2 days Re-start GSK3368715 at reduced dose if resolved $>$ 2 days Discontinue GSK3368715 if not resolved to Grade \leq 1 within \leq 14 days
	Grade 4	
 Supportive care as above, plus consider intravenous (IV) hydration, hospital admission and IV nutrition as appropriate Discontinue GSK3368715 if lasting $>$2 days despite supportive care
All Other Toxicity*	Grade 1	
 Continue dosing with no change
	Grade 2	
 Continue dosing with no change 
OR
 
 Hold GSK3368715 for up to 1 week for toxicity to be $<$ Grade 2, then continue at the same dose (dose reduction is required if the grade 2 toxicity is considered a DLT)

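### The PR and QTc stopping rules in Sections 7.1.4 and 7.1.2 disagree with Table 14, and the protocol does not say which ECG readings decide the QTcF rule

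*Protocol*

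**What the plan says.** **PR.** Protocol Section 7.1.4 gives the stopping criterion as "An increase in the PR interval to >250 msec in participants without pre-existing AV-block". The PR row of Table 14 in Appendix 12 reads "An increase in the PR Interval to >250 msec", bases the reading on the mean of the triplicate, and directs that GSK3368715 be discontinued. It mentions no exception for AV block. At entry, exclusion 8d bars "AV-block (asymptomatic 2nd degree Type II or 3rd degree and any degree AV block if related to heart disease or if symptomatic".

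**QTc.** Section 7.1.2 stops treatment on "QTcF > 500 msec" or "Change from baseline of QTc > 60 msec". It accepts either a single value or the triplicate average, and offers 5-10 minutes as an example of a brief recording period. The discontinuation row of Table 14 reads "If ≥ 60 msec change from baseline occurs OR QTcF ≥ 500 msec (average of three ECGs over at least 15 minutes".

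**Recording.** Section 8.2.3 spaces the three tracings at most 2 minutes apart and adds: "The full set of triplicates should be completed in less than 4 minutes".

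**Standing of the two places.** Appendix 12 describes its criteria as guidance that does not replace clinical judgment. Section 6.2, which introduces the same dose-modification guidelines, says that a direction to stop study treatment permanently is mandatory, and refers to Section 7.

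**The concern.** A stopping rule has to give one answer for one set of readings. Here two current parts of the protocol cover different populations for PR, and use different inequalities and different ECG readings for QTc. Two sites could follow the protocol faithfully and reach different decisions on the same tracing.

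PR and QRS prolongation are the cardiovascular risk named in the Section 2.3.1 risk table, and cardiac stopping criteria are one of the listed mitigations. Under Section 7.1, a participant who has permanently discontinued cannot be retreated, so the choice of rule cannot be undone for that participant. It also carries into the SAP displays of reasons for treatment discontinuation (Table 1.2) and AEs leading to discontinuation (Table 3.7), and possibly into the protocol deviation summary (Table 1.6).

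**Working it through.** No sample size, error rate or event count is involved, so the check sets the passages side by side.

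| Item | Section 7.1 | Table 14 | Section 8.2.3 |
|---|---|---|---|
| PR threshold | >250 msec | >250 msec | – |
| PR population | only those with no prior AV block | no restriction | – |
| QTcF absolute | >500 msec | ≥500 msec | – |
| QTc change | >60 msec | ≥60 msec | – |
| ECG basis for QTc | single or averaged | average of three | triplicate |
| Recording time for QTc | e.g. 5-10 min | at least 15 min | under 4 min in total |

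**Step 1, PR.** Exclusion 8d removes Type II second-degree block, third-degree block, and block of any degree that is symptomatic or related to heart disease. First-degree and Type I second-degree block remain eligible when asymptomatic and unrelated to heart disease, so the group that Section 7.1.4 exempts can be enrolled. Take such a participant with an on-treatment PR of 260 msec (an illustrative value). Table 14: 260 > 250, discontinue. Section 7.1.4: not applicable, no stop. At or below 250 msec, or with no prior AV block, the two places agree on the threshold.

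**Step 2, QTc inequality.** At a QTcF of exactly 500 msec, or a change of exactly 60 msec, Table 14 stops and Section 7.1.2 does not. At every other value the inequalities agree.

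**Step 3, single versus averaged value.** Suppose one tracing reads 500 + d msec and the other two average 500 − e msec, with d and e positive. The mean is

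[(500 + d) + 2(500 − e)] / 3 = 500 + (d − 2e)/3,

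which is below 500 whenever e > d/2. The single value then meets Section 7.1.2 while the average does not meet the absolute limit in Table 14. Table 14's averaging bracket follows the 500 msec limb, and the wording does not settle whether it also governs the 60 msec change.

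**Step 4, recording time.** Three tracings have two gaps, so the longest spacing under Section 8.2.3 is 2 × 2 = 4 minutes, and the set must finish in under 4. Table 14 asks for at least 15, a shortfall of more than 15 − 4 = 11 minutes. One set of three tracings cannot meet both. The 5-10 minute figure overlaps neither, but it is only an example and the argument does not need it.

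**Step 5, does rank settle it?** Calling Appendix 12 guidance would favour Section 7, but Section 6.2 makes directions for permanent discontinuation mandatory. Section 7.1 does not help either. Its list of reasons labels Section 7.1.4 as the clinical deterioration rules and does not name the PR criterion.

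**The case against.** The strongest reply concerns the recording time. The limit of under 4 minutes governs scheduled triplicates. Section 8.2.3 also points to Section 7.1.2 for further QTc readings that may be needed, and the row of Table 14 that allows dosing to continue speaks of manual QTcF. Table 14 could therefore describe a separate, manually read confirmatory set, and both rules could then be met. A reader might infer that a triplicate taken as instructed can never lead to a Table 14 QTcF decision; the documents do not support that. What stands is narrower: no section defines such a confirmatory set, and Section 7.1.2 gives no repeat procedure.

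A second reply is that the recording-time question does not touch PR. That is correct. The 5-10 and 15 minute periods are attached to QTc only, and the PR row of Table 14 gives no duration.

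A third is that Section 6.2 refers to Section 7, which could be read as ranking Section 7 first. The sentence can equally be read as giving Table 14's directions mandatory force, so it does not decide the matter. Nor does the Amendment 3 summary. It lists the Section 7.1.4 wording as updated text, but it also lists an edit to Table 14 (the VTE row), so one cannot simply assume that the table was left behind.

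The SAP does not resolve the conflict. Its QTcF and PR ranges in Section 14.8.1 are reporting flags, and its averaging of three ECGs in Section 5.4 is an analysis convention.

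**Conclusion.** The PR conflict is real in current text and gives opposite decisions, but only for a participant who enters with permitted AV block and then exceeds 250 msec. It does not affect everyone with AV block, and the documents do not say how many such participants there were. The QTc inequality is a boundary matter. The difference between single and averaged values, and the undefined 15-minute set, are the more substantial parts of the QTc discrepancy.

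The consequence is confined to discontinuation decisions and their reported reasons. A reader might infer that ECG-related AE counts also depend on the rule chosen. They do not follow from it: AEs rest on investigator-judged clinical significance (Appendix 3) and are graded by CTCAE. The ECG row of the DLT criteria (Table 6) names only QRS.

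Two assumptions are made. Discontinuation in the PR and QTcF rows of Table 14 is taken as permanent, since those rows contain no restart provision, unlike the VTE row. Exclusion 8d is read literally. No view is taken on which clinical rule is right.

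**What to change.** Reconcile Sections 7.1.2, 7.1.4, 8.2.3 and Table 14 so that they state:

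- the same PR population, with the AV-block exception present in both places or in neither;
- the same QTc inequality;
- the same ECG basis and recording window for QTcF, or an explicit statement that the Table 14 set is a separate confirmatory reading, and when it is taken.

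The choice among these belongs to the sponsor. The bullet in Section 7.1 that points to Section 7.1.4 should also name the PR criterion.

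The cost is wording in four protocol places, plus that bullet; reconciling text need not add a procedure. SAP Section 2.1 records that enrolment has ended. If no further amendment is planned, the clinical study report should state which rule and which ECG basis sites applied, and identify any discontinuation, or decision to continue, that would have differed under the other rule.

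The QRS criterion also differs, in msec in Section 7.1.3 and Table 6 but as a percentage in Table 14. That is a separate discrepancy, not relied on here, which could be reconciled in the same edit.
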